#### 9.3.2.2 Prior and Concomitant Medication

The FOPal registry study will collect the use of prior and concomitant medication including dose, frequency, start/end dates and reason for prescription at the Baseline Visit and at the Follow-up/End of Study Visits if available.

#### 9.3.2.3 Concomitant Surgery

The FOPal registry study will collect the following data on concomitant surgery at the Baseline Visit and at the Follow-up/End of Study Visits if available:

- Surgical procedure name;
- Indication:
- Reason for concomitant surgery;
- Date of surgery.

# 9.3.2.4 Linear Height and Weight

The FOPal registry study will collect linear height and weight for all participants at the Baseline Visit, at the first marketed palovarotene intake (for exposed non-naïve participants) and at the Follow-up/End of Study Visits (only if clinic visit) if available. Linear height within the past 6 to 12 months prior to the first palovarotene intake will also be collected if available.

PAGE 53 OF 287

9.3.2.5 Adverse Events, Special Situations, and Adverse Events of Special Interest for Exposed Participants

# Adverse Events and Special Situations

The FOPal registry study will collect the following AE data from the signing of the informed consent form (ICF) until last palovarotene intake + 30 days, and will include retrospective AEs from the first dose of marketed palovarotene intake for non-naïve participants:

- All AEs, TEAEs, irrespective of causality, including serious TEAEs, start/end date, time to onset, nature, severity, seriousness, causality assessment, any treatment administered for the AE, action taken and outcome (definitions, management and reporting of AEs are described in Section 11);
- Deaths, irrespective of causality, including date and cause of death;
- Special Situations (defined in Section 11.1.3), irrespective of causality, including start/end date, category, description, whether the Special Situation led to an AE and outcome.

Retrospective AE from the first marketed palovarotene intake and until the signed informed consent date will be collected as "Retrospective important medical events related to the disease (including vertebral fractures") as specified in Table 3.

If AEs or their sequelae (any AE, based on the investigator's opinion, not only those assessed as related) persist after the date of palovarotene discontinuation, the investigator must ensure that the participant receives appropriate medical follow up and this should be properly documented in the participant's medical records.

All participants discontinuing palovarotene treatment will be followed up in the registry up to 30 days after last palovarotene intake (unless consent is withdrawn).

#### Adverse Events of Special Interest

The FOPal registry study will collect the following AESIs:

- PPC;
- Fractures:
- Psychiatric AEs;
- Hepatic AEs;
- Convulsions AEs.

These events must be collected on the AE form of the eCRF according to the completion guideline and using the specific AESI reporting option.

If they meet the seriousness criteria, they should also be reported as SAEs.

## 9.3.2.6 *Medical Events of Special Interest for Unexposed Participants*

The FOPal registry will collect medical events within 12 months preceding the signed informed consent, at Baseline Visit and at the Follow-up/End of Study Visits if available.

Medical events of special interest include, but are not limited to:

- Growth outcomes, including PPC;
- Fractures.

**PAGE 54 OF 287** 

# 9.3.2.7 Safety Variables

Vital Signs

The FOPal registry study will collect respiratory rate, blood pressure and heart rate at the Baseline Visit, at the first marketed palovarotene intake (for exposed non-naïve participants) and at the Follow-up/End of Study Visits (only if clinic visit) if available.

#### **Growth Status**

The FOPal registry study will collect bone age, knee height and epiphyseal status ("open/partially closed/closed/not assessable") for growing children at the Baseline Visit, at the first marketed palovarotene intake (for exposed non-naïve participants) and at the Follow-up/End of Study Visits if available.

Growing children are those in whom the growth plates have not fused. Whether the participant is a growing child is based on the investigator's assessment.

# Tanner Staging

The FOPal registry study will collect Tanner stage (rating of development of secondary sex characteristics; pubic hair, testicular volume, breast development, where Stage 1 corresponds to the pre-pubertal form and Stage 5, the final adult form [35]) for growing children at the Baseline Visit, at the first marketed palovarotene intake (for exposed non-naïve participants) and at the Follow-up/End of Study Visits if available.

# Pregnancy Testing for Exposed Participants

Participants will be assessed for child-bearing status and pregnancy prevention measures prior to receiving palovarotene. As per local label, pregnancy testing will be carried out with a confirmation of absence of pregnancy for as long as the participant receives palovarotene and for one month after stopping. These conditions also apply to participants who are not currently sexually active unless the prescriber considers that there are compelling reasons to indicate that there is no risk of pregnancy.

Pregnancy is contraindicated during treatment with palovarotene, therefore if a participant is pregnant or has a positive pregnancy test at any time during the registry study, this will result in immediate discontinuation of palovarotene. A pregnant participant will be followed throughout her pregnancy and through the first year postpartum to monitor pregnancy-related AEs and the birth and developmental outcomes of the infant(s)' through the first year of life (see Section 11.1.3.1).

#### Spinal Health Assessment for Exposed Participants

The FOPal registry study will collect the outcome/results of radiological imaging and the type of imaging used to assess the participants' spinal health status in clinical practice, as recommended by the product label. The type of radiological imaging techniques for which outcomes/results will be collected include, but are not limited to, CT, X-ray and scintigraphy.

#### *Fractures (including vertebral fractures)*

The FOPal registry study will collect the severity and descriptive details of any fractures (including vertebral fractures) in the SAE eCRF page from the signed informed consent date. For exposed non-naïve participants, any fractures that occurred between the first marketed palovarotene intake and the signed informed consent date will be recorded at the Baseline Visit using a different form. For unexposed participants, any fractures occurring within 12 months preceding the signed informed consent date and during the study will be recorded using the medical events of special interest eCRF pages.

**PAGE 55 OF 287** 

#### 9.3.2.8 Effectiveness Variables

Cumulative Analogue Joint Involvement Scale

The CAJIS for FOP will be collected at the Baseline Visit and at the Follow-up/End of Study Visits (only if a clinic visit) if available.

The CAJIS is an objective measure of joint movement completed by the investigator to document total joint involvement [36]. This scale, which was developed by the investigators from the Center for Research in FOP and Related Disorders, assesses functional disability by categorising ROM across 12 joints (both right and left shoulder, elbow, wrist, hip, knee and ankle joints) and three body regions (cervical spine, thoracic/lumbar spine and jaw), with each joint/region assessed as: 0=normal (<10% deficit); 1=partially impaired (10% to 90% deficit); 2=functionally ankylosed (>90% deficit). The CAJIS total score is calculated as the sum of the scores of all joints/regions and ranges from 0 (no involvement) to 30 (maximally involved).

The examiner must also note and record (yes/no) if the participant:

- Can walk;
- Uses a wheelchair;
- Needs some help with activities of daily living;
- Needs complete help with activities of daily living.

Use of Assistive Devices and Adaptations for Daily Living

The use of assistive devices and adaptations for daily living will be collected at the Baseline Visit and at the Follow-up/End of Study Visits if available.

The questionnaire will be filled in by the participant or the proxy as per below table:

Questionnaire	If participant is an Adult (≥15 years)	If participant is a Child (<15 years) Filled by	
	Filled by		
	Participant	Participant	Proxy
FOP assistive devices assessment (Version 1.0)	X*		X

\* If participants are unable to answer on their own, an individual can be involved and reports only the participant's response on their behalf.

FOP=Fibrodysplasia Ossificans Progressiva.

In case of PRO completion by an individual (if participants are unable to answer on their own), the recommendations for such administration are detailed below:

- The individual should be different from a healthcare professional and should be the same across multiple assessments.
- The individual must only report the participant's response without any amendments or interpretation.

Assistive devices and adaptations for daily living (including healthcare utilisation) include:

- Mobility aids;
- Eating tools;
- Personal care tools;
- Bathroom aids and devices;
- Bedroom aids and devices;
- Home adaptations;

**PAGE 56 OF 287** 

- Work environment adaptations;
- Technology adaptations;
- Sports and recreation adaptations;
- School adaptations;
- Medical therapies for daily living;
- Healthcare utilisation.

#### Physical and Mental Function

Physical function as assessed by the age-appropriate forms of the FOP-PFQ and physical and mental function (overall QoL for participants <15 years old) as assessed by the age-appropriate forms of the PROMIS Global Health Scale will be collected at the Baseline Visit and at the Follow-up/End of Study Visits if available.

Questionnaires will be filled in by the participant or the proxy as per below table:

Questionnaires	If participant is an	If participant is a	
	Adult (≥15 years)	Child (<15 years)	
	Filled by	Filled by	
	Participant	Participant	Proxy
FOP-PFQ assessment – (8-14) years –			X
proxy questionnaire (Version 1.0)			Λ
FOP-PFQ assessment – (8-14) years – self		X*	
questionnaire (Version 1.0)		Λ	
FOP-PFQ assessment – adult questionnaire	X*		
(Version 1.0)			
PROMIS Global Health Scale –			
(8- 14) years – proxy questionnaire			X
(Version 1.0)			
PROMIS Global Health Scale –			
(8- 14) years – self questionnaire		X*	
(Version 1.0)			
PROMIS Global Health Scale – adult	X*		
questionnaire (Version 1.2)	Λ.		

\* If participants are unable to answer on their own, an individual can be involved and reports only the participant's response on their behalf.

FOP-PFQ=FOP-Physical Function Questionnaire; PROMIS=Patient-Reported Outcomes Measurement Information System.

In case of PRO completion by an individual (if participants are unable to answer on their own), the recommendations for such administration are detailed below:

- The individual should be different from a healthcare professional and should be the same across multiple assessments.
- The individual must only report the participant's response without any amendments or interpretation.

The FOP-PFQ is a disease-specific patient-reported outcome measure of physical impairment which includes questions related to activities of daily living and physical performance. There are adult and paediatric versions of the FOP-PFQ; the adult form should be used for participants 15 years and older and for participants under 15 years old, there is a self-completed paediatric

**PAGE 57 OF 287** 

form (developed for participants 8 to 14 years old) and a proxy-completed paediatric form (developed for participants 5 to 14 years old).

The FOP-PFQ consists of 28 questions in the adult version and 26 questions in the paediatric version which are scored on a scale of 1 to 5, with lower scores indicating that the participant has more difficulty completing those tasks. Score calculations are described in Section 9.7.3.3.

PROMIS Global Health Scale is a patient-reported outcome measure of physical and mental function in participants ≥15 years old and overall QoL for participants <15 years old. There are adult and paediatric versions of the PROMIS Global Health Scale; the adult form should be used for participants 15 years and older and for participants under 15 years old, there is a self-completed paediatric form (developed for participants 8 to 14 years old) and a proxy completed paediatric form (developed for participants <15 years old).

The PROMIS Global Health Scale consists of 10 questions in the adult version and 9 questions in the paediatric version. For the adult form, two scores are calculated: the global physical health score and the global mental health score, both ranging from 4 (worse health) to 20 (better health). For the paediatric form, only a total score is calculated, ranging from 7 (worse health) to 35 (better health). All scores are converted to T-scores, with a higher T-score value indicating better health. Score calculations and conversion to T-scores are described in Section 9.7.3.3.

# Lung Function Parameters

Lung function parameters will be collected at the Baseline Visit and at the Follow-up/End of Study Visits (only if clinic visit) if available.

The lung function parameters of observed FVC (litres) and % predicted FVC, observed  $FEV_1$  (litres) and % predicted  $FEV_1$  and the absolute and % predicted  $FEV_1$ /FVC ratio are obtained by spirometry.

The parameters of observed (traditional unit of mL/min/mmHg or SI unit of mmol/min/kPa) [37] and % predicted DLCO is obtained by the DLCO test. This provides information on the efficiency of gas transfer from alveolar air into the bloodstream. Carbon monoxide (CO) has a high affinity for haemoglobin and it follows the same pathway as that of oxygen to finally bind with haemoglobin. Inhaled CO is used for this test due to its high affinity for haemoglobin which is 200-250 times that of oxygen [38].

#### Flare-ups

At Baseline, the investigator will ask the participant how many flare-ups they experienced over the past 12 months. At each Follow-up Visit, the investigator will ask the participant how many flare-ups they experienced since the last visit.

#### Movement Mobility Change

For each movement mobility change, the impacted location, start date, causes, the outcome (change in extra bone growth, change in movement and associated flare-up event, if any) at the Baseline Visit and Follow-up/End of Study associated Visits if available. Movement mobility history over the past 12 months prior to the Baseline Visit will also be collected at the Baseline Visit.

Symptoms associated with flare-ups include, but are not limited to, pain, swelling, stiffness, redness, warmth, fever, lethargy, loss of appetite, decreased range of motion and change in mood or behaviour.

At each visit, the investigator will ask the participant if they experienced any movement mobility change since their last visit.

**PAGE 58 OF 287** 

#### 9.3.2.9 Treatment Variables for Exposed Participants

The registry study will collect the following data on chronic and flare-up palovarotene treatment at the Baseline Visit and at the Follow-up/End of Study Visits if available:

- Dose and frequency of palovarotene for chronic and flare-up treatment;
- Dose modifications, interruptions, start date and end date.

#### 9.4 Data Sources

Source data includes any data collected as part of routine medical care which will be captured in an eCRF by the investigator and transmitted to the sponsor for analysis. The patient-reported questionnaires (FOP-PFQ, PROMIS Global Health Scale and FOP assistive devices assessment) will be completed directly by the participant or proxy on paper (see Section 9.3.2.8).

In observational studies like FOPal, data collection relies on several stakeholders: 1) investigators and site staff; 2) Healthcare professionals (HCPs) including general practitioners (GP), paediatrician, other physicians and home nurses; and 3) patients. Sponsor consultation with physicians who are expert in managing FOP confirms that in the real-world setting, while formal in-person visits may be scheduled annually, patients are also in contact with these experts throughout the year on an ad hoc basis for many aspects of FOP care. Active data collection is only managed via the sites and the sponsor has multiple strategies to ensure the sites regularly provide structured data collection. This active data collection process is summarised in Figure 3.

[figure not shown]

Figure 3 Active data collection process flow

Abbreviations: GP= General practitioner, HCP= Healthcare professional, PI= Principal Investigator.

# 9.5 Registry Study Size

The FOPal registry study aims to enrol a minimum of 67 participants with FOP treated with palovarotene and 33 participants with FOP not treated with palovarotene. Approximately half of the participants in each cohort (exposed and unexposed) will be paediatric (8 years to less than 18 years of age for girls and 10 years to less than 18 years of age for boys).

**PAGE 59 OF 287** 

#### 9.6 Data Management

Data management for FOPal will be conducted by a Service Provider (SP) directed by the sponsor's Global Medical Affairs Biometry Department. All data management procedures will be completed in accordance with the Standard Operating Procedures (SOPs) of Ipsen and the contracted SP.

## 9.6.1 Data Collection

The specific data to be collected at each visit, if available, are summarised in the Schedule of Assessments (Table 2, Table 3 and Table 4).

All relevant data collected as part of routine medical care will be captured using the eCRF by the investigator (patient-reported questionnaires will be completed directly by the participant or proxy on paper and returned to the site for data entry into the eCRF) and transmitted to the sponsor. If some assessments are not routinely performed by the investigator, they will not complete the corresponding sections in the eCRF.

Data will be collected in an eCRF via the internet utilising a secured website. The sponsor and the SP will ensure that the eCRF developed is appropriate to capture the data required by the protocol. The sponsor will ensure that the entrusted SP uses adequate technology to ensure data security transfer and backup.

Each site is required to have a computer and internet connection available for site entry of clinical data. Data entry in the eCRF will be performed by the investigator or by the designated person from their team and to ensure confidentiality and security of the data, all entries into the eCRF will be made under the electronic signature (e-signature) of the person performing the action (username and password). Only sponsor-authorised users will be given access to the eCRF as appropriate for their study responsibilities. All users must have successfully undergone software application training prior to entering data into the eCRF.

Once written informed consent (and assent, if applicable) has been obtained, the eCRF will provide a numeric participant identifier to pseudonymise the data from each participant. Data for each participant must be entered into the eCRF within 5 days of the participant's enrolment, each Follow-Up Visit and the End of Study Visit. Data transmitted will be pseudonymised and will be identified only by the participant number. Only investigating sites will be able to link the numeric identifier to each participant's identity.

In compliance with Good Pharmacoepidemiology Practices (GPP), the participant's medical records should be clearly marked and permit easy identification of their participation in this study.

Medical and surgical history, non-drug therapies, concomitant surgeries, Special Situations and AE terms will be coded using the Medical Dictionary for Regulatory Activities (MedDRA) and prior/concomitant medication will be coded using the World Health Organization Drug Dictionary (WHODD) by the contracted SP and reviewed by the sponsor.

Queries will be edited in English and addressed to the investigational site using the eCRF and will be answered by investigators or authorised registry study staff members directly into the eCRF.

The eCRF will be signed electronically by the investigator to certify that all the data recorded in it are consistent with the source documents and reflect the status of the participant during the corresponding part of the registry study.

PAGE 60 OF 287

# 9.6.2 Data Archiving and Retention

During the site initiation visits, the monitor must ensure that the archiving facilities are adequate and archiving/retention responsibilities of the investigator have been discussed.

The FOPal registry study documents should be retained for at least 15 years after registry study completion. However, these documents should be retained for a longer period if required by the applicable regulatory requirements or by agreement with the sponsor. The investigator should take measures to prevent accidental or premature destruction of these documents. The final archiving arrangements will be confirmed by the monitor when closing-out the site. The sponsor will inform the investigator, in writing, as to when these documents no longer need to be retained.

If the investigator relocates or retires, or otherwise withdraws their responsibility for maintenance and retention of registry study documents, the sponsor must be notified (preferably in writing) so that adequate provision can be made for their future maintenance and retention.

# 9.7 Data Analysis

# 9.7.1 Analyses Population Definitions

For the purposes of analyses, the following populations are defined:

- Enrolled Population including all participants who signed the ICF.
- Safety Exposed Population including all enrolled participants who have taken at least one dose of marketed palovarotene at any time before the signed ICF or during the study; A distinction will be made depending on time of start of marketed palovarotene:
  - Palovarotene prevalent users: participants who received palovarotene before or at the time of ICF signed;
  - Palovarotene incident users: participants who started receiving palovarotene after enrolment in the registry. Two time periods will be defined: Period 1 is from enrolment to last day before the first dose of marketed palovarotene; Period 2 is after the first dose of marketed palovarotene.
- Safety Exposed Paediatric Population including all paediatric participants (8 years to less than 18 years of age for girls and 10 years to less than 18 years of age for boys) from the Safety Exposed Population.
- Safety Unexposed Population including all enrolled participants who never received at least one dose of marketed palovarotene before or during their participation in the registry;
- Safety Unexposed Paediatric Population including all paediatric participants (8 years to less than 18 years of age for girls and 10 years to less than 18 years of age for boys) from the Safety Unexposed Population.

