# 9.1 Registry Study Design

FOPal is an observational, prospective and retrospective registry study designed to collect and assess real-world safety data on paediatric and adult participants with FOP exposed to palovarotene and secondly to describe the effectiveness of palovarotene in exposed participants. Additionally, key safety outcomes (i.e. flare-up episodes, growth and bone fractures) will be descriptively compared in participants with FOP exposed and unexposed to palovarotene enrolled in the FOPal registry.

Exposed and unexposed participants will be recruited in countries/sites willing to participate and where palovarotene is registered/marketed. For exposed participants, the decision to prescribe palovarotene will be made prior to and independently of the decision to enrol the patient in the FOPal registry study.

Participants who started palovarotene treatment before the implementation of the registry study in their country may also be enrolled. All participants who received at least one dose of palovarotene treatment before enrolling in the registry study (i.e. signing the informed consent) will be considered non-naïve. In such context, some data will be collected retrospectively from the first dose of marketed palovarotene intake. A schematic representation of the different data collection scenarios is shown Figure 2.

Figure 2 Schematic representation of the different scenarios applied for prospective and retrospective data collection from participants enrolled in the FOPal registry

The schedule of assessments in Table 2 and Table 3 describes the type of data collected for exposed naïve and non-naïve participants, respectively, from the first dose of marketed palovarotene intake. The schedule of assessments in Table 4 describes the type of data collected for unexposed participants from up to 12 months before the ICF signature. The details are described in the Section 9.2.7.

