### 9.2 Setting

Paediatric and adult participants with FOP who are enrolled in the FOPal registry and have received at least one dose of palovarotene, prescribed as per local label, by their treating physician will be included in the palovarotene-exposed cohort. Paediatric and adult participants with FOP who are enrolled in the FOPal registry and have never received palovarotene, will be included in the palovarotene-unexposed cohort.

Individuals who do not meet the criteria for participation in the FOPal registry study (screen failure) or who withdraw their consent may be rescreened. Rescreened participants should be assigned a new participant number. The informed consent process is described in Section 9.13.

PAGE 37 OF 287

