# 9.2.1 Palovarotene-exposed Cohort

#### 9.2.1.1 Inclusion Criteria

To be included in the palovarotene-exposed cohort, the participants should fulfil all the following inclusion criteria:

- (1) Paediatric (8 years to less than 18 years of age for girls and 10 years to less than 18 years of age for boys) and adult participants with FOP who have been prescribed palovarotene (prior to and independently of the decision to enrol the patient in the FOPal registry study) by their treating physician, as per local label;
- (2) Signed informed consent as per local regulations must be obtained and maintained. Consent/assent from the participant should be obtained as appropriate before any registry study data collection is conducted. If applicable, parents or legally authorised representatives must give signed informed consent.

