#### 9.2.2.2 Exclusion Criteria

Participants will not be included in the palovarotene-unexposed cohort if:

- (1) Currently participating in any interventional clinical trial;
- (2) Previously received palovarotene, other synthetic oral retinoids, or any disease modifying therapy for the reduction of heterotopic ossification.

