# 9.2.3 Registry Study Population

Paediatric and adult participants with FOP who are enrolled in the FOPal registry and have received at least one dose of palovarotene, prescribed, as per local label, by their treating physician will be included in the palovarotene-exposed cohort. Participants never treated with palovarotene will be included in the palovarotene-unexposed cohort.

To be enrolled, participants must comply with all the inclusion criteria (Section 9.2.1.1 and Section 9.2.2.1 for the palovarotene-exposed and unexposed cohorts, respectively) and exclusion criteria (Section 9.2.1.2 and Section 9.2.2.2 for the palovarotene-exposed and unexposed cohorts, respectively).

PAGE 38 OF 287

The FOPal registry study aims to enrol a minimum of 67 participants with FOP treated with palovarotene (exposed) and 33 participants with FOP not treated with palovarotene (unexposed) from countries/sites willing to participate. Approximately half of the participants in each cohort (exposed and unexposed) will be paediatric (8 years to less than 18 years of age for girls and 10 years to less than 18 years of age for boys).

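### Section 9.7.1 defines the unexposed comparator by absence of a marketed dose alone, so a prescribed participant who never starts could enter it without being screened against the unexposed criteria

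*Protocol*

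**What the plan says.** Three parts of the protocol bear on who counts as unexposed.

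**Entry to the exposed cohort.** Inclusion criterion 1 in section 9.2.1.1 covers paediatric and "adult participants with FOP who have been prescribed palovarotene". No dose has to have been taken. Section 9.2 describes the same cohort as those who "have received at least one dose of palovarotene, prescribed as per local label, by their treating physician will be included in the palovarotene-exposed cohort", and section 9.2.3 repeats the dose requirement.

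**Entry to the unexposed cohort.** Section 9.2.2.2 excludes anyone who meets this description: "Previously received palovarotene, other synthetic oral retinoids, or any disease modifying therapy for the reduction of heterotopic ossification". That bars earlier palovarotene from any source, not only the marketed product.

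**Analysis populations.** Section 9.7.1 counts everyone who signed the consent form as enrolled. It requires at least one marketed dose for the Safety Exposed Population, and gives the complement as "Safety Unexposed Population including all enrolled participants who never received at least one dose of marketed palovarotene". Neither definition mentions the cohort of entry. Section 9.7.3.4 then uses the Safety Unexposed Population as the comparator in the inverse-probability-weighted comparison of key safety outcomes.

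**The concern.** The population rule is looser than the cohort rule it should mirror. Section 9.2.2.2 screens for three kinds of earlier treatment; section 9.7.1 tests for one product from one source. For people enrolled under 9.2.2 the gap does no harm, because they were screened at entry. It matters for someone who enters the exposed cohort on a prescription and never starts, since that person was never checked against 9.2.2.2.

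Earlier treatment is plausible in this disease. Section 7.3.1 reports 164 people exposed to palovarotene in the clinical studies, against an estimated prevalence of 1.36 per million (section 7.1). Section 9.2.7.1 records previous use of the investigational product for exposed naïve participants without excluding them. Growth is one of the compared outcomes, and section 7.3.1 reports premature physeal closure in 27 of 102 participants under 18. A former trial participant counted as unexposed would blur the contrast on the outcome where a drug effect is of most interest. The covariates named for the propensity score (age, gender, time since last flare-up, total CAJIS score) do not include earlier treatment, although others may be added.

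**Working it through.** **Step 1: can a person be enrolled in the exposed cohort undosed?** Under 9.2.1.1, yes. Section 9.1 labels as non-naïve "All participants who received at least one dose of palovarotene treatment before enrolling in the registry study", so exposed naïve participants consent first. Section 9.7.1 also provides for "participants who started receiving palovarotene after enrolment in the registry", with a Period 1 that runs up to the day before the first marketed dose.

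**Step 2: where does that person go if no marketed dose follows?** Not into the Safety Exposed Population, which needs a marketed dose. By the wording of 9.7.1, into the Safety Unexposed Population.

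**Step 3: does another rule remove the person?** Not clearly.
- The withdrawal rule in 9.2.8 covers an exposed participant who is no longer receiving palovarotene. It does not describe one who never began.
- The rule on switchers in 9.7.3.4 covers people who start treatment after being unexposed, which is the reverse case.

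**Step 4: size.** Sections 9.5 and 9.7.2 plan a minimum of 67 treated and 33 untreated participants (67 + 33 = 100). They give no never-start rate, so the count k of never-starters is an assumption. Never-starters add to the 33 and displace nobody, so their share of the comparator is k/(33 + k):

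| k (assumed) | Comparator | Share |
|---|---|---|
| 0 | 33 | 0% |
| 1 | 34 | 1/34 = 2.9% |
| 2 | 35 | 2/35 = 5.7% |
| 3 | 36 | 3/36 = 8.3% |
| 4 | 37 | 4/37 = 10.8% |

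These shares count all never-starters. Those with earlier palovarotene, retinoid or disease-modifying therapy are a subset of unknown size. If more than 33 unexposed participants are enrolled, every share falls.

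**The case against.** **The protocol offers a contrary reading.** Sections 9.2 and 9.2.3 confine the exposed cohort to people who took a dose. Section 9.2.3 places those never treated in the unexposed cohort and requires every enrolee to meet the criteria of the cohort concerned. On that reading, a never-dosed person counted as unexposed must also satisfy 9.2.2.2. This stands as a reasonable view of the intent. It does not settle the matter, because 9.2.1.1 is the operative entry criterion and says something else.

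**Section 9.7.3.4 may already neutralise earlier trial treatment.** It ends unexposed follow-up at the first intake of any investigational or commercialised FOP treatment. If that intake came before consent, the end date precedes the index date and the person contributes no time. This is arguable, but it is an inference rather than a stated exclusion, and it does not reach oral retinoids taken for another indication.

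**Classification by actual exposure is normal for a safety population.** This stands. A never-starter with no earlier therapy is truly untreated. The remaining issue for such a person is selection for treatment, which the weighting is meant to address.

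**Two stronger inferences are tempting but not supported.**
- A reader might conclude that events in never-starters would be missed or not comparable, because the exposed naïve schedule (Table 2) lacks the medical-events row and 12-month retrospective column of Table 4. However, the comparison starts at the index date, which for unexposed participants is consent, so the look-back precedes it. Table 2 still collects 12-month flare-up history and an earlier height. Fractures and premature physeal closure are collected as adverse events of special interest after consent. Separate forms already distinguish the two whole cohorts by design.
- A reader might apply a never-start percentage to the 67 and treat the result as expected contamination. Section 9.7.2 counts the 67 as treated, so never-starters are not among them. Participants with a marketed dose before consent cannot contribute either.

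**Conclusion.** The point holds as a defect in a stated definition. Read literally, 9.7.1 together with 9.2.1.1 lets an unscreened, prescribed but never-dosed participant into the comparator, and no passage clearly prevents it. The documents do not show that this will happen often, or that those affected will have been treated before. The 3% to 11% range rests on an assumed 1 to 4 never-starters and an unexposed cohort at its minimum; the true figure may be zero.

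The consequence is confined to a secondary comparison that section 9.7.3.4 reports as estimates and confidence intervals without hypothesis testing. The primary safety endpoints are summarised in the Safety Exposed Population and are untouched. This is a low-severity correction, worth making because the comparator is small and the change is nearly free.

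**What to change.** 1. In 9.7.1, restrict the Safety Unexposed Population to participants enrolled under 9.2.2 who meet 9.2.2.2: no earlier palovarotene, marketed or investigational, no other synthetic oral retinoid and no disease-modifying therapy. Apply the same restriction to the paediatric subset.
2. State there that the time before treatment of unexposed enrolees who later start palovarotene is handled as in 9.7.3.4, which keeps such data when at least 6 months were collected. Without this, a never-received condition conflicts with that rule, as the present wording already does.
3. Report exposed-cohort enrolees without a marketed dose in the disposition table only.
4. Reconcile 9.2.1.1 with 9.2 and 9.2.3 on whether a prescription or a dose defines entry to the exposed cohort.

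The cost is a sentence or two in 9.7.1 and an aligned entry criterion. The planned minimum of 33 is unaffected. The downside is that a few truly untreated never-starters leave the comparison.
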